10.3.3. Recording and Follow-Up of AE and/or SAE

AE and SAE Recording

- When an AE/SAE occurs, it is the responsibility of the investigator to review all
 documentation (eg, hospital progress notes, laboratory reports, and diagnostics reports) related
 to the event.
- The investigator will then record all relevant AE/SAE information.
- It is **not** acceptable for the investigator to send photocopies of the participant's medical records in lieu of completion of the required form.
- There may be instances when copies of medical records for certain cases are requested. In this
 case, all participant identifiers, with the exception of the participant number, will be redacted
 on the copies of the medical records before submission.

 The investigator will attempt to establish a diagnosis of the event based on signs, symptoms, and/or other clinical information. Whenever possible, the diagnosis (not the individual signs/symptoms) will be documented as the AE/SAE.

Assessment of Severity

The investigator will assess intensity for each AE and SAE reported during the study.

All AEs observed will be graded using the National Cancer Institute (NCI) Common Terminology Criteria for Adverse Events (CTCAE) version 5.0.

The grade refers to the severity of the AE. If a particular AE's severity is not specifically graded by the guidance document, the investigator is to use the general NCI CTCAE definitions of grade 1 through grade 5 following his or her best medical judgment, using the following general guideline:

- Grade 1: Mild; asymptomatic or mild symptoms; clinical or diagnostic observations only; intervention not indicated.
- Grade 2: Moderate; minimal, local or noninvasive intervention indicated; limiting age-appropriate instrumental activities of daily living (ADL) (eg, preparing meals, shopping for groceries or clothes, using the telephone).
- Grade 3: Severe or medically significant but not immediately life-threatening; hospitalization or prolongation of hospitalization indicated; disabling; limiting self-care ADL (ie, bathing, dressing and undressing, feeding self, using the toilet, taking medications, and not bedridden).
- Grade 4: Life-threatening consequences or urgent intervention indicated.
- Grade 5: Death related to AE.

NOTE: An AE that is assessed as severe should not be confused with an SAE. Severe is a category used for rating the intensity of an event; and both AEs and SAEs can be assessed as severe.

An event is defined as "serious" when it meets at least 1 of the predefined outcomes as described in the definition of an SAE, not when it is rated as severe. Grade 4 and 5 AEs are always assessed as serious (ie, SAE).

Assessment of Causality

- The investigator is obligated to assess the relationship between IMP and each occurrence of each AE/SAE as **related** or **not related**. The investigator will use clinical judgment to determine whether there is reasonable possibility that the IMP caused the AE.
- A reasonable possibility of a relationship conveys that there are facts, evidence, and/or arguments to suggest a causal relationship, rather than a relationship cannot be ruled out.
- Alternative causes, such as underlying disease(s), concomitant therapy, and other risk factors, as well as the temporal relationship of the event to IMP administration, will be considered and investigated.
- Related means that the AE cannot be explained by the participant's medical condition, other
 therapies, or an accident. The temporal relationship between the AE and IMP administration is
 compelling and/or follows a known or suspected response pattern concerning that IMP.
- Not related means that the AE can be readily explained by other factors such as the participant's underlying medical condition, concomitant therapy, or accident. No plausible temporal or biologic relationship exists between the IMP and the AE.
- The investigator will also consult the investigator's brochure (IB) and/or product information, for marketed products, in his/her assessment.
- For each AE/SAE, the investigator **must** document in the medical notes that they have reviewed the AE/SAE and has provided an assessment of causality.
- There may be situations in which an SAE has occurred and the investigator has minimal
 information to include in the initial report. However, it is very important that the investigator
 always assess causality for every event before the initial transmission of the SAE data.

- The investigator may change his/her opinion of causality in light of follow-up information and send an SAE follow-up report with the updated causality assessment.
- The causality assessment is one of the criteria used when determining regulatory reporting requirements.

Follow-up of AEs and SAEs

- The investigator is obligated to perform or arrange for the conduct of supplemental
 measurements and/or evaluations as medically indicated or as requested to elucidate the nature
 and/or causality of the AE or SAE as fully as possible. This may include additional laboratory
 tests or investigations, histopathological examinations, or consultation with other health care
 professionals.
- If a participant dies during participation in the study or during a recognized follow-up period, the investigator will provide a copy of any postmortem findings including histopathology.
- New or updated information will be recorded in the originally submitted documents.
- The investigator will submit any updated SAE data within 24 hours of receipt of the information.

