- The participant develops any of the following, based on the sponsor's determination of relatedness:

- Any treatment-emergent adverse event (TEAE) of Common Terminology Criteria for Adverse Events (CTCAE) severity grade 4 that is considered related to IMP
- Any treatment-emergent SAE of grade 3 considered related to IMP
- Any infections of grade 3 or any serious infection considered related to IMP
- The participant develops any malignancy, either new or recurrent, other than basal cell carcinoma of the skin, regardless of relatedness.

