8.4.4. Reporting of AEs and SAEs

All AEs that occur during the study, from signing of the ICF until the EoTP or the last follow-up visit, are to be recorded on the appropriate AE pages (either "serious" or "nonserious") of the eCRF. The investigator should complete all the details requested, including date of onset, time of onset, stop date (when applicable), stop time (when applicable), severity, action taken, outcome, and relationship to IMP, to corticosteroid (non-IMP) use, and to study procedures. Each event should be recorded separately on the eCRF.

Any SAE, including death due to any cause, which occurs during this study after the signing of the ICF, whether or not related to the IMP, must be reported immediately (within 24 hours of the study site's knowledge of the event). Further information on follow-up procedures is provided in Section 8.4.3 and Section 10.3.

The report will contain as much available information concerning the SAE as possible, to enable the sponsor (or an authorized representative) to file a report, which satisfies regulatory reporting requirements. These timelines apply to initial reports of SAEs and to all follow-up reports.

Criteria for documenting the relationship to IMP and severity, outcome, and action taken will be the same as those previously described.

All SAEs that are spontaneously reported within 30 days after the last study visit are to be collected and reported in the safety database, and all efforts should be made to follow-up until resolution.

Additional follow-up information should be completed and entered on a paper SAE report form and sent by fax/email to the sponsor's designee.

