10.1.11.3. Study Closure

The sponsor can halt the study and conduct a review of safety data if any of the following occur during either part A or B:

- 2 or more participants have safety findings that are considered unacceptable for the study population
- 2 or more study participants have the same (or similar) severe AE that is considered to be related or possibly related to the IMP

In both of the cases noted above, the study may resume (with resumption of IMP administration) following the conclusion of a safety data review and a favorable recommendation by the DSMB.

Additionally, the sponsor can halt the study for any other reason.

If the study is prematurely terminated or suspended, the sponsor shall promptly inform the investigators, the IECs/IRBs, the regulatory authorities, its designee, and any vendors used in the study of the reason for termination or suspension, as specified by the applicable regulatory requirements. The investigator shall promptly inform the participant and should assure appropriate participant therapy and/or follow-up.

The study can also be terminated by the regulatory authority for any reason.

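### Protocol 10.3.3 gives two incompatible tests for the binary causality rating, so an adverse event with both a plausible IMP link and a competing cause has no consistent classification

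*Protocol*

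**What the plan says.** Protocol 10.3.3 (Assessment of Causality) offers two categories only, related and not related: "The investigator is obligated to assess the relationship between IMP and each occurrence of each AE/SAE as" one or the other. It sets the test in these terms: "The investigator will use clinical judgment to determine whether there is reasonable possibility that the IMP caused the AE". It then explains the phrase: "A reasonable possibility of a relationship conveys that there are facts, evidence, and/or arguments to suggest a causal relationship". Being unable to rule a link out is expressly not enough. Alternative causes, concomitant therapy among them, are to be considered and investigated.

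Two definitions follow. For the first category: "Related means that the AE cannot be explained by the participant's medical condition, other therapies, or an accident". A second sentence adds compelling timing and/or a known or suspected response pattern for the IMP. The definition of *not related* asks that other factors readily explain the event, and adds that there is no plausible temporal or biologic link with the IMP.

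Elsewhere, protocol 8.4.4 has the investigator record "relationship to IMP, to corticosteroid (non-IMP) use, and to study procedures" for each event. SAP 5.1.3 tabulates treatment-related and prednisone-related events separately. SAP 5.1.2 says how a missing relatedness field is filled but does not define relatedness. Protocol 10.1.11.3 lets the sponsor halt the study for a safety review if "2 or more study participants have the same (or similar) severe AE that is considered to be related or possibly related to the IMP".

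**The concern.** The first test asks for positive evidence that the IMP contributed. The *related* definition asks that nothing else could account for the event. Two investigators can each follow section 10.3.3 faithfully and rate the same event differently.

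This matters here because the protocol itself supplies both explanations for infection. Table 2 and section 8.4.7 describe lowered IgG as a route to increased infection risk. Section 8.3.7 names immunosuppressive and immunomodulatory therapy as able to trigger or aggravate infections. Section 6.8.1 gives every participant in both arms prednisone or an equivalent oral corticosteroid.

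The rating feeds several outputs:

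- the SAP 5.1.3 tables of treatment-related TEAEs, serious TEAEs, grade 3 or higher TEAEs and AESIs;
- regulatory reporting, for which 10.3.3 names causality as one of the criteria;
- the liver chemistry criteria in 7.1.1 and 7.1.2, where permanent discontinuation turns on the investigator's judgement of relatedness.

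**Working it through.** No arithmetic applies; the check is to put one event through each rule in 10.3.3.

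**Test case.** An infection on IMP for which the investigator sees evidence of an IMP contribution, and for which the concurrent corticosteroid is also a credible explanation.

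| Wording in 10.3.3 | What it requires | Result for the test case |
|---|---|---|
| Reasonable possibility | Facts, evidence or arguments suggesting causation; other causes weighed | Related |
| Definition of *related* | No explanation from medical condition, other therapies or accident | Cannot be related |
| Definition of *not related*, first sentence | Readily explained by other factors | May be met |
| Definition of *not related*, second sentence | No plausible temporal or biologic link | Fails, so not *not related* |

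1. The first two rows give opposite answers for the same event.
2. Rows two to four together leave the event in neither category, although the scale has only two. The two definitions are therefore not exhaustive. There is also a gap in threshold: one turns on whether another explanation exists at all, the other on whether it explains the event readily.
3. The recording scheme in 8.4.4 keeps IMP and corticosteroid relationship as separate items, so an event can be attributed to both. The reasonable-possibility test allows that. Read literally, the *related* definition does not, because an event explained by the corticosteroid is explained by another therapy.
4. Neither the protocol nor the SAP gives a precedence rule. The only SAP provision, treating missing relatedness as related, does not act on a rating that was entered under one reading or the other.
5. The halt criterion in 10.1.11.3 uses a possibly-related category that the two-point scale never records, so the two sections do not share a vocabulary.

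**The case against.** The best reply is that the *related* bullet only elaborates the main test. Its second sentence admits events that follow a suspected response pattern for the IMP, which infection does. Merely taking a corticosteroid does not mean the corticosteroid explains the event, and clinical judgement fills the gap. Separate corticosteroid attribution shows that dual attribution was intended. Part of this stands: co-administration alone does not disqualify an event, and the reasonable-possibility test is itself demanding, since it needs positive evidence. But the second sentence adds to the exclusion requirement and does not replace it. Where the corticosteroid is a credible explanation, judgement is still being asked to apply two opposing standards. Intended practice does not change the wording that sites are given.

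The reply is right about reach, and three stronger readings should be resisted.

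- A reader might infer that the conflict governs stopping IMP for infection, through "Any infections of grade 3 or any serious infection considered related to IMP". Section 7.1.1 bases that criterion on the sponsor's determination, not directly on the investigator's rating.
- A reader might infer that an infection signal would be hidden. All events in the infections class are AESIs whether related or not (8.4.7), they are tabulated by arm regardless of causality (SAP 5.1.3), and the DSMB sees unblinded participant-level safety data (10.1.5). Table 2 lists serious infection as a potential risk; the documents do not call it the main identified risk.
- A reader might infer that the halt criterion is disabled. It already includes related events, its other limb needs no relatedness, and the sponsor may halt for any reason.

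**Conclusion.** The contradiction is real and lies in current protocol text. It is an inconsistency in definition that makes relatedness-based outputs depend on which sentence a site applies. It touches the treatment-related tables, regulatory reporting and the investigator-judged liver criteria. Efficacy, type I error, sample size, all-causality safety tables, DSMB review and the sponsor-determined discontinuation criteria are not directly affected.

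The size of any misclassification cannot be computed: the documents give no infection rate and nothing on how sites would choose between the wordings. Time on corticosteroid might look like a substitute, but it measures only how long a competing explanation is available, not how many events are misrated. The likely direction, if sites apply the exclusion wording literally, is fewer events rated as related. The conclusion assumes only that some events have both a plausible IMP link and a credible alternative cause, which the protocol's own account of infection makes reasonable.

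**What to change.** In protocol 10.3.3, keep reasonable possibility as the single criterion and rewrite the two definitions to follow it:

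- *Related*: there is a reasonable possibility that the IMP caused the event, even if another cause may also have contributed.
- *Not related*: there is no such reasonable possibility.

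Add a sentence that an event may be attributed to both IMP and corticosteroid, and carry it into the eCRF completion guidance.

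Separately, 10.1.11.3 and 10.3.3 must be reconciled, because the halt criterion uses a category that the rating scale does not contain. This point does not propose how the halt criterion should read; simply trimming it to the recorded categories could narrow it.

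The cost is protocol wording and site guidance. The downside is that more events may be reported as treatment-related. Ratings made before the change will have been made under the conflicting text, and the study report should say so where treatment-related tables combine the two.

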10.3.4. Reporting of SAEs and AESIs

SAE and AESI Reporting

- All SAEs and AESIs will be recorded on the AE form of the eCRF. SAEs will also be recorded on the paper SAE report form.
- The investigator or designated site staff should check that all entered data are consistent.
- An alert email for the SAE/AESI report on the eCRF will then automatically be sent by email to the sponsor's designee safety mailbox via the EDC system.
- The paper SAE report form should be faxed or emailed to the sponsor's designee (refer to the Serious Adverse Event Reporting details on page 2 of this protocol).

10.4. Appendix 4: Contraceptive and Barrier Guidance

10.4.1. Women of Childbearing Potential Definition

A woman is considered to be of childbearing potential (WOCBP) unless she is either:

- a. Postmenopausal: A postmenopausal state is defined by continuous amenorrhea for at least 1 year without an alternative medical cause with an FSH measurement of >40 IU/L. If a postmenopausal woman is using hormonal therapy, such as hormone replacement therapy or hormonal contraceptives, FSH levels might be suppressed; therefore, an FSH test to confirm a postmenopausal state is not considered valid. In a case such as this, the postmenopausal state will need to be assessed by the investigator.
- b. Surgically sterilized: Women who have had a documented permanent sterilization procedure (eg, hysterectomy, bilateral salpingectomy, or bilateral oophorectomy)

10.4.2. Contraception Guidance

10.4.2.1. Female Contraception for Women of Childbearing Potential

WOCBP must use 1 of the following contraception methods from the time of signing the ICF until the date of their last dose of IMP.

[figure not shown]
- 1. Combined (estrogen- and progestogen-containing) hormonal contraception associated with inhibition of ovulation:
 - a. Oral
 - b. Intravaginal
 - c. Transdermal
- 2. Progestogen-only hormonal contraception associated with inhibition of ovulation:
 - a. Oral
 - b. Injectable
 - c. Implantable
- 3. Intrauterine device (IUD)
- 4. Intrauterine hormone-releasing system (IUS)
- 5. Bilateral tubal occlusion
- 6. Vasectomized partner
- 7. Sexual abstinence: a highly effective method only if defined as refraining from heterosexual intercourse during the entire period of risk associated with the IMP. The reliability of sexual abstinence needs to be evaluated in relation to the duration of the study and the preferred and usual lifestyle of the participant
- 8. Progestogen-only oral hormonal contraception in which inhibition of ovulation is not the primary mode of action
 - a. Oral
 - b. Injectable
 - c. Implantable

- 9. Male or female condom with or without spermicide
- 10. Cap, diaphragm, or sponge with spermicide

10.4.2.2. Male Contraception

No male contraception is required.

10.5. Appendix 5: The Karnofsky Performance Index

[figure not shown]
treatment of carcinoma. Cancer 1:634-656, 1948.

10.6. Appendix 6: Investigator Global Assessment of Bullous Pemphigoid (IGA-BP)

It is not necessary that all characteristics under morphological descriptors be present to meet criteria for an IGA score.

[figure not shown]
Score	*Morphological Descriptors

10.7. Appendix 7: Bullous Pemphigoid Disease Area Index (BPDAI) Questionnaire

[figure not shown]

[figure not shown]
Copyright © 2011 University of Pennsylvania; All Rights Reserved

10.8. Appendix 8: The Itch Numerical Rating Scale (Itch NRS)

[figure not shown]

10.9. Appendix 9: The EuroQol 5-Dimension 5-Level (EQ-5D-5L)

[figure not shown]

10.10. Appendix 10: Dermatology Life Quality Index (DLQI)

[figure not shown]

[©]AY Finlay, GK Khan, April 1992 www.dermatology.org.uk, this must not be copied without the permission of the authors.

10.11. Appendix 11: Autoimmune Bullous Disease Quality of Life (ABQoL) Questionnaire

Thank you for taking the time to complete this questionnaire

10.12. Appendix 12: The Glucocorticoid Toxicity Index

Table 14: GTI 2.0 Composite Index (Adapted for ARGX-113-2009)

Domain	Score
	_
	_
	-
	-
_	_
	1
	 

Table 14: GTI 2.0 Composite Index (Adapted for ARGX-113-2009) (Continued)

Source: Adapted from McDowell et al. 2021.³⁹

argenx

BMI=body mass index; GTI=Glucocorticoid Toxicity Index; HbA1c=glycated hemoglobin; LDL=low-density lipoprotein; NP=neuropsychiatric

Table 15: GTI 2.0 Specific List (Adapted for ARGX-113-2009)

[figure not shown]

Table 15: GTI 2.0 Specific List (Adapted for ARGX-113-2009) (Continued)

Source: Adapted from McDowell et al. 2021.39

BMI-body mass index; GTI=Glucocorticoid Toxicity Index

^a For the reasons described in Section 8.3.9, bone mineral density will not be assessed in ARGX-113-2009. Therefore, the bone health parameter "bone mineral density decrease >6%" has been removed from this list.

10.13. Appendix 13: Country-Specific Requirements

The following lists modifications to the protocol's existing text that are required for specific countries. Cross-references to applicable sections of the protocol are included with each item.

10.13.1. Japan

A Japanese patient is defined as a patient who was born in Japan and currently lives in Japan with Japanese nationality, has not lived outside of Japan for a total of >10 years, and whose parents and 4 grandparents are Japanese.

10.13.2. China

PD and immunogenicity blood samples that are collected from participants in China at screening may be used to develop and validate methods to support the efgartigimod development program. Such use of these samples is only permitted after obtaining approval from the Human Genetic Resources Administration of China (HGRAC), and the methods in which they are used must comply with local regulations. Additionally, the conditions in which these samples are stored and ultimately destroyed must comply with HGRAC requirements and other relevant regulations (Section 8.6 and Section 8.9).

In China, oral methylprednisolone will be provided instead of oral prednisone (Section 6.8.1.3). For concurrent oral methylprednisolone dose adjustment regimen, refer to Table 16.

Table 16: Concurrent Oral Methylprednisolone Equivalent Doses (in mg) Based on Participant Body Weight

Table 16:	Concurrent Oral N	lethyl	predn	isolor	ıe Equ	iivalei	nt Dos	es (in	mg) E	sased (on Pai	rticipa	ant Bo	dy W	eight
		Body weight category ^a													
	<45 kg	≥45 to <50 kg	≥50 to <55 kg	≥55 to <60 kg	≥60 to <65 kg	≥65 to <70 kg	≥70 to <75 kg	≥75 to <80 kg	≥80 to <85 kg	≥85 to <90 kg	≥90 to <95 kg	≥95 to <100 kg	≥100 to <105 kg	≥105 to <110 kg	≥110 kg
Oral prednisone dose level	Minimum recommended daily methylprednisolone doses					Daily	methy	predni	solone	doses ^b					Maximum recommended daily methylprednisolone doses
mg/kg/day								mg/day	7						
1.0	32	36	40	44	48	52	56	60	64	68	72	76	80	84	88
0.75	24	24	28	32	36	36	40	44	48	48	52	56	60	60	64
Starting dose: 0.50	16	18	20	20	24	24	28	28	32	32	36	36	40	40	48
0.30	10	10	12	12	14	14	16	18	18	20	20	20	24	24	32
0.20	6	6	8	8	8	10	10	12	12	12	14	14	16	16	20
0.15	4	4	6	6	6	6	8	8	8	10	10	10	12	12	14
Minimal OCS therapy: ≤0.10	2	2	4	4	4	4	4	6	6	6	6	6	8	8	10
mg/day	mg/day														
7.5	NA	NA	NA	NA	NA	NA	NA	NA	NA	NA	NA	NA	6	6	6
5.0	NA	NA	NA	NA	NA	NA	NA	4	4	4	4	4	4	4	4
2.5	NA	NA	2	2		2	2	2	2	2	2	2	2	2	2
Off OCS therapy:	0	0	0	0	0	0	0	0	0	0	0	0	0	0	0

NA=not applicable; OCS=oral corticosteroids (oral methylprednisolone)

Notes: Each new dosage must be maintained for at least 2 weeks provided that no new lesions (transient or nontransient) appear. Duration of tapering steps from escalated doses (>0.5 mg/kg/day) may be shortened based on clinical judgment.

- ^a Body weight should be rounded to the nearest whole number.
- ^b The investigator should not deviate from the recommended concurrent oral methylprednisolone dosing regimen, except in matters where the safety of the participant may be compromised.

